Version and date of protocol: version 5, date: 07/18/2023

Study Protocol

Official Title: The effectiveness of chatbot facilitated education
on child and adolescent abuse for nurses

Protocol ID: IRB112-148-B

ClinicalTrails.gov ID: NCT06167031

Project PI : [name]

Project Co-PI : [name], [name]

Version/Date: version 5, 18/07/2023

Background

The incidence of child and adolescent abuse and neglect (CAN) is increasing both in Taiwan and globally. As frontline healthcare professionals, nurses play a pivotal role in the early identification and reporting of CAN. However, research indicates that insufficient knowledge and limited competency among nursing staff can impede timely recognition and notification of suspected cases. Strengthening nurses' knowledge and competencies in assessing and reporting CAN is therefore essential. With the advancement of technology, continuing nursing education has expanded beyond traditional lecture-based formats. In particular, online education has gained momentum since the COVID-19 pandemic, offering flexible, accessible learning opportunities. Chatbots, as a form of individualized digital learning, have emerged as a promising tool for enhancing nurses' ability to recognize and report CAN.

Objective

The study aims to evaluate the effectiveness of chatbot-facilitated education in assisting nursing personnel to prevent CAN. This evaluation will focus on the impact of this learning on CAN competency.

Method

An experimental study design was employed. Participants were purposively sampled and allocated to the experimental and control group. The experimental group received chatbot-facilitated education (CFE), while the control group received conventional lecture-based instruction. The course content, developed using the ADDIE instructional design model, comprised two modules: (1) Child and Adolescent Abuse and Neglect and (2) Nurses' Roles and Responsibilities in CAN. The *CAN Knowledge and Competency Scale* was used to measure learning outcomes at three time points: pre-intervention, one week post-intervention, and four weeks post-intervention.

Statistical Analysis Plan

The collected questionnaire data will be coded and analyzed using the SPSS for Mac version 29.0.1.0 statistical software package. The statistical analysis methods employed will include descriptive statistics and inferential statistics (Table 1-1). A significance level of $p < .05$ will be used for hypothesis testing.

1. Descriptive Statistics

The central tendency and dispersion trends of the sample will be presented using frequency distribution, percentage, mean, and standard deviation to understand the distribution of the sample's basic attributes.

2. Inferential Statistics

(1) Chi-square test (χ^2 test)

- a. To test whether there are statistically significant differences in categorical variables between the two groups.

(2) Independent-samples t-test

- a. To test whether there are statistically significant differences in continuous variables between the two groups.
- b. To test whether the average scores of CAN intention to report, attitude toward reporting, and knowledge evaluations between the two groups are statistically significantly different.

(3) Paired-samples t-test

- a. To test whether there are statistically significant differences in CAN intention to report, attitude toward reporting, and knowledge evaluations within each group over three time points.

(4) Generalized Estimating Equation (GEE)

- a. To test whether there are statistically significant differences in CAN intention to report, attitude toward reporting, and knowledge evaluation scores between the two groups across different time points.

Table 1-1 Research hypotheses and analysis methods (1/2)

Research hypotheses	Assessment tool	Analysis methods	Statistical methods
1-1-1. There are differences in the intention to report CAN across three assessments within both the experimental and control groups.	CAN Knowledge and Competency Scale	IV: Different assessment time points DV: Scores for the intention to report CAN, attitude toward reporting CAN, and knowledge of CAN	Paired-sample t-test
2-1-1. There are differences in the attitude toward reporting CAN across three assessments within both the experimental and control groups.			
3-1-1. There are differences in the knowledge of CAN across three assessments within both the EG and CG.			
1-1-2. There are differences in the intention to report CAN across three assessments between the experimental and control groups.	CAN Knowledge and Competency Scale	IV: Group DV: Pre-test, post-test 1, and post-test 2 scores for the intention to report CAN, attitude toward reporting CAN, and knowledge of CAN	Independent-samples t-test
2-1-2. There are differences in the attitude toward reporting CAN across three assessments between the experimental and control groups.			
3-1-2. There are differences in the knowledge of CAN across three assessments between the experimental and control groups.			

CAN: child and adolescent abuse and neglect; EG: experimental group; CG: control group; IV: independent variable; DV: dependent variable.

Table 1-1 Research hypotheses and analysis methods (2/2)

Research hypotheses	Assessment tool	Analysis methods	Statistical methods
1-1-3. There are differences in the improvement scores for intention to report CAN between the experimental and control groups.	CAN Knowledge and Competency Scale	IV: Group and different assessment time points DV: Scores for the intention to report	Generalized estimating equation (GEE)
2-1-3. There are differences in the improvement scores for attitude toward reporting CAN between the experimental and control groups.		CAN, attitude toward reporting CAN, and knowledge of CAN	
3-1-3. There are differences in the improvement scores for knowledge of CAN between the experimental and control groups.			

CAN: child and adolescent abuse and neglect; EG: experimental group; CG: control group; IV: independent variable; DV: dependent variable.

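### The protocol describes no random assignment to chatbot or lecture, and unless allocation was random, differences between the nurses in each arm can pass for a chatbot effect.

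*Combined protocol and SAP*

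**What the plan says.** The Method section opens with "An experimental study design was employed" and continues "Participants were purposively sampled and allocated to the experimental and control group". That second sentence is the whole account of assignment. The arms follow: "The experimental group received chatbot-facilitated education (CFE), while the control group received conventional lecture-based instruction". Outcomes are measured "pre-intervention, one week post-intervention, and four weeks post-intervention". The title and the Objective both frame the study as one of effectiveness.

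The Statistical Analysis Plan uses a chi-square test, "To test whether there are statistically significant differences in categorical variables between the two groups", and an independent-samples t-test, "To test whether there are statistically significant differences in continuous variables between the two groups". It gives no action to take if the groups differ. Table 1-1 (1/2) compares the groups by independent-samples t-test at the pre-test and at each post-test. For the improvement hypotheses (1-1-3, 2-1-3, 3-1-3), Table 1-1 (2/2) gives the GEE inputs as "IV: Group and different assessment time points DV: Scores for the intention to report" and the other two scores. No covariate is listed.

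Neither the protocol nor the analysis plan mentions randomisation, sequence generation, concealment, stratification or matching.

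**The concern.** The contrast of improvement between arms is the trial's answer to its objective. It can be read as the effect of the teaching method only if the nurses in the two arms would otherwise have improved alike. Random assignment secures that in expectation. The word experimental does not, because it names no procedure.

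The comparison here makes the point more than formal. One arm uses an individual digital tool and the other a lecture. Motivation, experience and comfort with technology could plausibly influence both the arm a nurse enters, if anyone chooses it, and how much she gains. If arms were chosen, a better result with the chatbot could reflect who received it. The bias could also run the other way and hide a real effect.

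The planned analysis would not rescue such a comparison. Tests of baseline variables describe imbalance without removing it, and nothing in the plan acts on their result.

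**Working it through.** **Step 1: what each planned analysis would remove if allocation was not random.**

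- *Chi-square and t-tests of baseline variables:* they remove nothing.
- *Between-group t-tests at post-test 1 and post-test 2 (hypotheses 1-1-2, 2-1-2, 3-1-2):* they remove nothing. Even a fixed starting gap in score passes straight into the comparison.
- *GEE on group and time (hypotheses 1-1-3, 2-1-3, 3-1-3):* the improvement hypotheses imply a group-by-time contrast. That removes a stable gap in starting score. It does not remove a difference in learning rate, or regression to the mean from unequal baselines.

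**Step 2: how much a bias in gain would matter.** The plan gives no sample size, SD, effect size or power, so it has no figure to reproduce. The only input from the documents is the .05 level that "will be used for hypothesis testing". Everything else is assumed: two-sided testing, equal variances, a pre-post correlation of 0.6, arm sizes of 30, 50 and 80, and a true chatbot effect of zero.

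Assumed route to bias: (arm difference in motivation, in SD) × (gain per SD of motivation).

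- Low: 0.5 × 0.2 = 0.10 SD
- High: 0.8 × 0.4 = 0.32 SD

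SD of the gain, in units of the score SD: √(2(1 − 0.6)) = √0.8 = 0.894.

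Standardised bias: d = b / 0.894, so b = 0.1, 0.2, 0.3 gives d = 0.112, 0.224, 0.335.

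Noncentrality: d × √(n/2), on 2n − 2 degrees of freedom. For n = 50, √25 = 5, giving 0.559, 1.118 and 1.677 on 98 df.

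False-positive rate from the noncentral t:

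| Nurses per arm | b = 0 | b = 0.1 SD | b = 0.2 SD | b = 0.3 SD |
|---|---|---|---|---|
| 30 | 5.0% | 7.1% | 13.6% | 24.8% |
| 50 | 5.0% | 8.6% | 19.8% | 38.2% |
| 80 | 5.0% | 10.8% | 29.0% | 55.9% |

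The b = 0 column is what random allocation gives in expectation.

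**Step 3: the unadjusted post-test t-test.** If the arms differ by b SD in the post-test score itself, the standard error in SD units is √(2/n). By the normal approximation, with n = 50, b = 0.1, 0.2, 0.3 and 0.5 SD give 7.9%, 17.0%, 32.3% and 70.5%. With n = 100 they give 10.9%, 29.3%, 56.4% and 94.2%.

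In both calculations a larger sample makes the false-positive rate worse, because it sharpens the estimate of a biased quantity. Step 2 tests one gain score, not the three-time-point GEE, so it indicates scale and does not reproduce the planned test.

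**The case against.** The strongest objection is that the documents do not say assignment was non-random. A reader might infer that it was, taking the adverb in the allocation sentence to govern both verbs, or picturing staff placing nurses by preference, ward or shift. The text does not support either inference. The adverb clearly describes the sampling and covers the allocation on only one reading. Purposive recruitment followed by random allocation is a coherent design, and the experimental label is compatible with it. No placement rule is mentioned, and nothing suggests that nurses knew their arm before the pre-test. This objection stands, and the point is therefore conditional.

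Second, the bias figures are assumptions throughout. They show what a bias would do, not that one exists, and zero bias fits the text if allocation was random. This also stands.

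Third, the Method section is written in the past tense, so allocation may already be complete. A new prospective randomisation sentence could then misdescribe what was done. This stands and shapes the fix.

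Fourth, the pre-test and the GEE give some protection. That is true for a stable starting gap, but the protection does not reach learning rate or the post-test t-tests.

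What survives all four is that a study of effectiveness describes no random assignment and plans no adjustment that would compensate for its absence.

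**Conclusion.** The point holds in conditional form and should be resolved before any between-group result is interpreted. The documents describe no randomisation, the post-test t-tests are unadjusted, and the GEE lists group and time only. Unless allocation was in fact random, the comparison mixes teaching method with differences between the nurses.

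The size is illustrative. At 50 per arm and a pre-post correlation of 0.6, a bias in gain of 0.1 to 0.3 SD takes a nominal 5% test to about 9% to 38%. Across the assumed arm sizes of 30 to 80, the range is about 7% to 56%.

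It would go too far to conclude that the trial is non-randomised or that its result cannot support a claim of effectiveness. That depends on a fact the documents do not give.

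**What to change.** First establish how and when nurses were assigned. Then take the branch that applies.

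**(a) Nurses are still to be assigned.** Keep purposive recruitment and replace the allocation sentence with, for example: *After consent and completion of the pre-test, each nurse is assigned 1:1 to chatbot-facilitated education or lecture by a computer-generated list in randomly varying blocks, prepared in advance and concealed from recruiting staff until the pre-test is submitted.* The direct cost is a wording change and a list. The downsides are that some nurses will not get the format they prefer, and that colleagues in different arms may share content.

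**(b) Allocation is complete and was random.** State how the sequence was generated and concealed, and whether the pre-test came before the arm was known. The cost is a few sentences.

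**(c) Allocation is complete and was not random.** Call the design quasi-experimental and report the group-by-time result as an association. Add to the GEE, as named covariates, the baseline characteristics that the descriptive statistics section already plans to summarise. Because baseline levels alone do not address learning rate, let these covariates interact with time. Base between-group conclusions on that model rather than on the unadjusted post-test t-tests. The documents do not list these characteristics or show that motivation or digital skill is measured, so the report should acknowledge both as possible remaining confounders. The cost is a more modest claim and a slightly larger model.

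### Does a bare p < .05 rule, with no deciding GEE test named, mean the three improvement hypotheses are not tested at 5%?

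*Combined protocol and SAP*

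**What the plan says.** The opening paragraph of the Statistical Analysis Plan sets a single threshold for all tests: "A significance level of $p < .05$ will be used for hypothesis testing". Table 1-1 (2/2) lists hypotheses 1-1-3, 2-1-3 and 3-1-3, one per outcome. The one for intention reads "There are differences in the improvement scores for intention to report CAN between the experimental and control groups", and the other two follow the same form. All three are assigned to GEE, with the entry "IV: Group and different assessment time points DV: Scores for the intention to report" and the other two outcomes listed after it. Item (4) under Inferential Statistics describes the GEE as a test of the three outcomes, ending with "knowledge evaluation scores between the two groups across different time points".

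The Method section places the assessments "at three time points: pre-intervention, one week post-intervention, and four weeks post-intervention". The row of Table 1-1 (1/2) for independent-samples t-tests lists the visits one by one: "IV: Group DV: Pre-test, post-test 1, and post-test 2 scores for the intention to report CAN". The GEE row does not.

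The plan does not write out the interaction term, name a deciding post-test or a joint test, rank the outcomes, or state a multiplicity rule. It gives no sample size.

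**The concern.** If time is categorical, three assessments give two between-group contrasts in change from pre-test for each outcome, at week 1 and at week 4. Each improvement hypothesis is a single statement that names neither week. If software prints both contrasts and each is compared with .05, the threshold belongs to the contrast and not to the hypothesis. When only one of the two is significant, the plan does not say whether the hypothesis is supported, so the choice could follow the results. A gain at week 1 and a gain kept to week 4 are also different claims.

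The Objective adds to the worry. It has a single aim, "This evaluation will focus on the impact of this learning on CAN competency", while the outcomes are unranked, so one significant contrast out of six might be presented as proof of effectiveness.

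**Working it through.** **Inputs from the documents.** Level .05; three assessments; three outcomes; one GEE hypothesis per outcome; non-directional wording, so two-sided tests are taken.

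**Assumptions.** The documents give no correlations, sample size or effect size. Error rates below are large-sample and assume no true effect.

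**1. The plan's own figure.** One two-sided test with critical value 1.96 has size 0.0500. A joint group-by-time test on 2 df has critical value −2 ln(0.05) = 5.991 and also has size 0.0500; 2,000,000 simulated draws gave 0.050. On either single-test reading, .05 is the error rate of the hypothesis.

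**2. Two contrasts per hypothesis.** Let r01, r04 and r14 be the correlations between pre-test and week 1, pre-test and week 4, and week 1 and week 4. The two changes from pre-test then have correlation

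(r14 − r01 − r04 + 1) / (2√((1 − r01)(1 − r04))).

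With a common correlation r this is (1 − r) / (2(1 − r)) = 0.5. The bivariate normal at 0.5 gives P(both significant) = 0.0093. Hence:
- either one: 0.05 + 0.05 − 0.0093 = 0.0907
- exactly one: 0.0907 − 0.0093 = 0.0814

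Over 651 admissible sets of visit correlations from 0.1 to 0.9, the either-one figure runs from 0.061 to 0.0975.

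| Rule for one hypothesis | False-positive rate (common visit correlation) |
|---|---|
| Joint 2-df test | 5.0% |
| One contrast named in advance | 5.0% |
| Either contrast suffices | 9.1% |
| Both contrasts required | 0.9% |

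**3. Three outcomes together.** With one joint test each and independent outcomes, 1 − 0.95³ = 0.143. At an assumed between-outcome correlation of 0.7 this falls to about 0.11. Counting any of six contrasts gives 24.8% at between-outcome correlation 0 and 19.2% at 0.7. That range needs two rules the plan does not contain: that either week suffices, and that any one outcome suffices.

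**4. What the remedies would cost.** Take 40 per arm, a true effect of 0.5 SD at both post-tests and visit correlation 0.5, all assumed. The standard error of a contrast is √((2/40) × 2 × (1 − 0.5)) = 0.2236, so the expected z is 0.5 / 0.2236 = 2.236.
- One named contrast: Φ(2.236 − 1.96) = 61% power.
- Joint test: noncentrality 2.236² × 2 / (1 + 0.5) = 6.67, which gives 63% power.
- Joint test at .05/3, the first Holm step: critical value −2 ln(0.05/3) = 8.19, which gives 46% power.
- Either contrast at .05: 77% power, with the 9.1% error rate above.

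**5. The text against the two readings.** Each GEE hypothesis is one non-directional statement tied to one method, with group and time as factors. A joint group-by-time test answers such a statement directly. Two week-specific contrasts are also compatible with it. Nothing in the table or in item (4) settles the matter, so the 9.1% figure describes one possible use of the plan and not its stated rule.

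**The case for a change.** The strongest case for a change is that the rest of Table 1-1 already answers single hypotheses with several tests. Hypothesis 1-1-1 covers all three assessments but is assigned to paired t-tests, each of which compares only two occasions. Hypothesis 1-1-2 is assigned to t-tests at each visit. Neither row has a rule for combining the results, and the GEE row does not announce a different approach. A split result is not rare either: under no effect exactly one contrast is significant in 8.1% of trials. With true effects of 0.3 or 0.5 SD, 30 to 100 per arm and visit correlations of 0.3 to 0.7 (all assumed), the two contrasts fall on opposite sides of .05 in 1% to 33% of trials. A few sentences in the SAP would settle it.

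Part of this stands. The deciding test is not written down, and the pattern of the t-test rows makes week-by-week reporting plausible. It does not show that the GEE hypotheses will be decided that way. The t-tests cannot be joint tests over three visits; the GEE can. The suggested repair would also leave the test to the investigators' own choice, so it adds a detail and corrects no error.

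The case for adjusting across outcomes is weaker. The plan numbers intention, attitude and knowledge as separate series of hypotheses and states no rule by which one success establishes overall effectiveness. The case for adjustment therefore depends on a claim the plan does not make.

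**Conclusion.** The claim that .05 is not the error rate of these hypotheses does not hold. With a joint group-by-time test, or one post-test contrast fixed in advance, it is 5.0% per hypothesis. It rises to about 9.1% (6.1% to 9.75%) only if either week is allowed to count, a rule the plan does not contain. What remains is an unwritten detail. An analyst can follow the plan soundly by fitting group, categorical time and their interaction, judging each hypothesis by the joint interaction test, and showing both weekly differences so that a split result is visible.

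Across outcomes, the 11% to 14% chance of at least one false positive matters only if a single overall claim is drawn. Protecting against it is a fair trade-off and not a necessity: in the illustration the first Holm step lowers joint-test power from 63% to 46%.

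The error rates assume large samples. The small-sample behaviour of robust Wald tests is a separate matter that affects the joint test too. The power figures rest on assumed sizes, effects and correlations, because the documents give none. No change to the plan is called for.

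### Nurse attributes are apparently tested between arms but used in no outcome analysis, so the GEE keeps imbalance in attributes that affect change, and the post-test t-tests keep imbalance in attributes related to score level.

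*Combined protocol and SAP*

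**What the plan says.** Section 1 (Descriptive Statistics) summarises the sample "to understand the distribution of the sample's basic attributes". The individual attributes are not listed.

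Section 2 (Inferential Statistics) gives a chi-square test in item (1)a, "To test whether there are statistically significant differences in categorical variables between the two groups", and an independent-samples t-test in item (2)a, "To test whether there are statistically significant differences in continuous variables between the two groups". The outcome scores have their own item, (2)b. The significance level is .05. No text says what follows from a significant or non-significant result of (1)a or (2)a.

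Table 1-1 sets out the outcome analyses:
- The between-group t-tests (1-1-2, 2-1-2, 3-1-2) have "IV: Group DV: Pre-test, post-test 1, and post-test 2 scores".
- The GEE (1-1-3, 2-1-3, 3-1-3) has "IV: Group and different assessment time points". Its first hypothesis reads "There are differences in the improvement scores for intention to report CAN between the experimental and control groups".
- The paired t-tests have assessment time only.

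No covariate appears in any row. The Method section says that nurses were sampled purposively and then assigned to two groups. It states no random method, stratification or ratio.

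**The concern.** The attribute tests serve no purpose in the plan. If allocation was random, a significant result only flags chance. If it was not, the test may detect a real difference, which then stays in the estimate. A non-significant result does not show that the arms are comparable, because the tests have limited power at modest sample sizes.

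At stake is the comparison of chatbot education with the lecture. If, for example, more experienced nurses learn more (or less) from any course and are unevenly spread, part of the between-arm difference in improvement reflects who was in each arm. The post-test t-tests are more exposed, because they also carry differences that existed before the course. Attributes that predict gain could also reduce the standard error, and the plan makes no use of them for that.

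**Working it through.** **Inputs.** From the documents: three assessments (before, one week after, four weeks after), alpha .05, and GEE terms for group and time only. The documents give no sample size, SD, attribute list or correlation, so there is no stated figure to reproduce. Assumed here: one attribute, 0.3 SD higher in one arm (d = 0.3); correlation r with the gain of 0.1, 0.3 or 0.5; 30, 50 or 100 nurses per arm (n); no true effect; complete data; two-sided tests.

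**1. What cancels.** Let attribute x shift a nurse's score by a·x at every visit and by a further b·x after the course. The change is (a·x + b·x) − a·x = b·x. The between-arm difference in mean change is therefore shifted by b × imbalance, and a drops out. A post-test difference is shifted by (a + b) × imbalance.

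A simulated GEE confirms this (exchangeable working correlation, robust standard error, 50 per arm, imbalance 0.5 SD, 300 replicates, true effect 0):

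| Attribute acts on | GEE group-by-time, unadjusted | With main effect | With attribute-by-time | Last-visit t-test |
|---|---|---|---|---|
| level only (a = 0.5) | 0.00 | 0.00 | 0.01 | 0.24 |
| change only (b = 0.3) | 0.14 | 0.14 | −0.01 | 0.14 |

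The expected values are 0.5 × 0.5 = 0.25 for the t-test in the first row and 0.5 × 0.3 = 0.15 for the unadjusted contrasts in the second. An attribute entered only as a main effect leaves the group-by-time estimate unchanged.

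**2. Shift in the improvement contrast.** Shift = r × d: 0.1 × 0.3 = 0.03, 0.3 × 0.3 = 0.09 and 0.5 × 0.3 = 0.15 SD of the gain.

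**3. Rejection rate with no true effect.** With complete data the contrast is a difference in mean change. Its noncentrality is r·d·√(n/2), referred to a t distribution with 2n − 2 degrees of freedom. For r = 0.5 and n = 30 this is 0.15 × √15 = 0.581, which gives 8.8%.

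| n per arm | r = 0.1 | r = 0.3 | r = 0.5 |
|---|---|---|---|
| 30 | 5.2% | 6.4% | 8.8% |
| 50 | 5.3% | 7.3% | 11.5% |
| 100 | 5.5% | 9.7% | 18.4% |

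The rate rises with n because the shift is fixed while the standard error shrinks. Regressing the gain on group and the attribute gave 4.8 to 5.2% in all nine cells (20,000 simulated trials each).

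**4. What the attribute test detects.** Its noncentrality is d·√(n/2), that is 1.162, 1.500 and 2.121. The imbalance reaches p < .05 in 21%, 32% and 56% of trials.

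**5. Standard error after adjustment.** Adjustment multiplies the variance by 1 − r². The imbalance itself adds a collinearity cost. The ratio of adjusted to unadjusted standard error is √[(1 − r²)(1 + (d² + 2/n)·n/(4(n − 1)))]. At n = 50 the second factor is 1 + 0.13 × 50/196 = 1.033, so the ratios are 1.011, 0.970 and 0.880 for r = 0.1, 0.3 and 0.5. Across the three sample sizes the change runs from about 1% larger at r = 0.1 to about 12% smaller at r = 0.5.

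**The case against.** A reader might infer that the GEE contrast keeps every attribute imbalance. The documents do not support that. The GEE hypotheses concern improvement, and step 1 shows that effects constant over visits cancel. Only attributes that affect change remain, or attribute-related dropout, which was not examined here. The interaction term is not written out, however. If a group main effect were reported instead, level imbalance would stay in it too.

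A reader might also infer that precision is certainly being lost. It is not certain: at r = 0.1 adjustment makes the standard error slightly larger, and no document supports a particular correlation.

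Nor do the documents show that the arms differ or that allocation was non-random. They only fail to describe a random method. The error rates above need a systematic imbalance. With none expected, the error stays near 5% and only the precision argument is left.

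Adjustment can also be overdone. A simulation with one continuous, one binary and one five-level attribute (r = 0.3, d = 0.3, uncorrected robust standard error, normal reference, 10,000 trials) gave these rejection rates, adjusted against unadjusted: 7.3% against 7.0% at 30 per arm, 6.6% against 7.8% at 50, and 5.9% against 10.5% at 100. At the smallest size the adjustment brought no benefit. A five-level factor alone adds 4 × 2 = 8 time-interaction terms. This stands, and it limits the fix.

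Finally, reading (1)a and (2)a as attribute tests is an inference, though a strong one given the separate item for scores. The tests themselves bias nothing; replacing them is a reporting improvement.

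**Conclusion.** The point holds in limited scope. The attributes are described and apparently tested, the result feeds no analysis, no outcome analysis adjusts for them, and the documented allocation does not secure balance. The improvement contrast keeps imbalance in attributes that affect change. The post-test t-tests keep imbalance in any attribute related to score level, and are the more exposed analysis.

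Under the assumptions stated, the bias in the improvement contrast runs from negligible (r = 0.1) to a false-positive rate of about 9%, 12% and 18% at 30, 50 and 100 per arm (r = 0.5). The true imbalance and correlations are unknown, so confidence in the size is moderate at best. The change is worth making because it costs little.

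**What to change.** - Replace tests (1)a and (2)a with a table of attributes by arm, with standardised differences and no p-values.
- Before analysis, and without using baseline p-values, name one or two recorded attributes with few parameters that plausibly affect learning. Years of nursing experience or earlier training on the topic are examples, if recorded. Group a many-level factor such as clinical unit into few categories or leave it out.
- Write out the GEE mean model for 1-1-3, 2-1-3 and 3-1-3 with group-by-time, and enter each named attribute together with its time interaction. A main effect alone is not enough. If the arms are small, use a small-sample-corrected robust standard error or a t reference.
- Base the post-test between-group comparisons (1-1-2, 2-1-2, 3-1-2) on attribute-adjusted estimates from the same model.
- Report the unadjusted GEE and t-tests as sensitivity analyses.

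The cost is SAP wording and a few model terms: with three visits, two time-interaction terms for each single-parameter attribute, besides its main effect. No new data are needed. The downside is a few degrees of freedom, and a slight loss of precision if the attributes barely predict gain. Adjustment covers only attributes that were recorded; it does not replace a statement of how nurses were allocated.
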